Appendix O. Dermatology Life Quality Index (DLQI)

The aim of this questionnaire is to measure how much your skin problem has affected your life **OVER THE LAST WEEK**. Please tick one box for each question.

Question	Response		
1. Over the last week, how itchy, sore, painful or stinging has your skin been?	Very much A lot A little Not at all	   	
2. Over the last week, how embarrassed or self-conscious have you been because of your skin?	Very much A lot A little Not at all	   	
3. Over the last week, how much has your skin interfered with you going shopping or looking after your home or garden ?	Very much A lot A little Not at all	   	Not relevant 
4. Over the last week, how much has your skin influenced the clothes you wear?	Very much A lot A little Not at all	   	Not relevant 
5. Over the last week, how much has your skin affected any social or leisure activities?	Very much A lot A little Not at all	   	Not relevant 
6. Over the last week, how much has your skin made it difficult for you to do any sport ?	Very much A lot A little Not at all	   	Not relevant 

Question	Response		
7. Over the last week, has your skin prevented you from working or studying? If "no," over the last week how much has your skin been a problem at work or studying ?	Very much A lot A little Not at all	   	Not relevant 
8. Over the last week, how much has your skin created problems with your partner or any of your close friends or relatives ?	Very much A lot A little Not at all	   	Not relevant 
9. Over the last week, how much has your skin caused any sexual difficulties?	Very much A lot A little Not at all	   	Not relevant 
10. Over the last week, how much of a problem has the treatment for your skin been, for example by making your home messy, or by taking up time?	Very much A lot A little Not at all	   	Not relevant 

Please check you have answered EVERY question. Thank you.

Appendix P. SF-36

Please see SF-36, version 2.0.

Your Health and Well-Being

This survey asks for your views about your health. This information will help keep track of how you feel and how well you are able to do your usual activities. *Thank you for completing this survey!*

For each of the following questions, please mark an in the box that best describes your answer.

1. In general, would you say your health is:

Excellent ▼  1	Very good ▼  2	Good ▼  3	Fair ▼  4	Poor ▼  5
--	--	---	---	---

2. Compared to one year ago, how would you rate your health in general now?

Much better now than one year ago ▼  1	Somewhat better now than one year ago ▼  2	About the same as one year ago ▼  3	Somewhat worse now than one year ago ▼  4	Much worse now than one year ago ▼  5
---	--	--	---	---

3. The following questions are about activities you might do during a typical day.
Does your health now limit you in these activities? If so, how much?

	Yes, limited a lot	Yes, limited a little	No, not limited at all
a. Vigorous activities, such as running, lifting heavy objects, participating in strenuous sports	 1	 2	 3
b. Moderate activities, such as moving a table, pushing a vacuum cleaner, bowling, or playing golf	 1	 2	 3
c. Lifting or carrying groceries	 1	 2	 3
d. Climbing several flights of stairs	 1	 2	 3
e. Climbing one flight of stairs	 1	 2	 3
f. Bending, kneeling, or stooping	 1	 2	 3
g. Walking more than a mile	 1	 2	 3
h. Walking several hundred yards	 1	 2	 3
i. Walking one hundred yards	 1	 2	 3
j. Bathing or dressing yourself	 1	 2	 3

4. During the past 4 weeks, how much of the time have you had any of the following problems with your work or other regular daily activities as a result of your physical health?

	All of the time	Most of the time	Some of the time	A little of the time	None of the time
a. Cut down on the amount of time you spent on work or other activities	 1	 2	 3	 4	 5
b. Accomplished less than you would like	 1	 2	 3	 4	 5
c. Were limited in the kind of work or other activities	 1	 2	 3	 4	 5
d. Had difficulty performing the work or other activities (for example, it took extra effort)	 1	 2	 3	 4	 5

5. During the past 4 weeks, how much of the time have you had any of the following problems with your work or other regular daily activities as a result of any emotional problems (such as feeling depressed or anxious)?

	All of the time ▼	Most of the time ▼	Some of the time ▼	A little of the time ▼	None of the time ▼
a. Cut down on the amount of time you spent on work or other activities	 1	 2	 3	 4	 5
b. Accomplished less than you would like	 1	 2	 3	 4	 5
c. Did work or other activities less carefully than usual	 1	 2	 3	 4	 5

6. During the past 4 weeks, to what extent has your physical health or emotional problems interfered with your normal social activities with family, friends, neighbors, or groups?

Not at all ▼	Slightly ▼	Moderately ▼	Quite a bit ▼	Extremely ▼
 1	 2	 3	 4	 5

7. How much bodily pain have you had during the past 4 weeks?

None ▼	Very mild ▼	Mild ▼	Moderate ▼	Severe ▼	Very Severe ▼
 1	 2	 3	 4	 5	 6

8. During the past 4 weeks, how much did pain interfere with your normal work (including both work outside the home and housework)?

Not at all ▼	Slightly ▼	Moderately ▼	Quite a bit ▼	Extremely ▼
 1	 2	 3	 4	 5

9. These questions are about how you feel and how things have been with you during the past 4 weeks. For each question, please give the one answer that comes closest to the way you have been feeling. How much of the time during the past 4 weeks:

	All of the time ▼	Most of the time ▼	Some of the time ▼	A little of the time ▼	None of the time ▼
a. Did you feel full of life?	 1	 2	 3	 4	 5
b. Have you been very nervous?	 1	 2	 3	 4	 5
c. Have you felt so down in the dumps that nothing could cheer you up?	 1	 2	 3	 4	 5
d. Have you felt calm and peaceful?	 1	 2	 3	 4	 5
e. Did you have a lot of energy?	 1	 2	 3	 4	 5
f. Have you felt downhearted and depressed?	 1	 2	 3	 4	 5
g. Did you feel worn out?	 1	 2	 3	 4	 5
h. Have you been happy?	 1	 2	 3	 4	 5
i. Did you feel tired?	 1	 2	 3	 4	 5

10. During the past 4 weeks, how much of the time has your physical health or emotional problems interfered with your social activities (like visiting friends, relatives, etc.)?

All of the time ▼	Most of the time ▼	Some of the time ▼	A little of the time ▼	None of the time ▼
 1	 2	 3	 4	 5

11. How TRUE or FALSE is each of the following statements for you?

	Definitely true ▼	Mostly true ▼	Don't know ▼	Mostly false ▼	Definitely false ▼
a. I seem to get sick a little easier than other people	 1	 2	 3	 4	 5
b. I am as healthy as anybody I know	 1	 2	 3	 4	 5
c. I expect my health to get worse	 1	 2	 3	 4	 5
d. My health is excellent	 1	 2	 3	 4	 5

THANK YOU FOR COMPLETING THESE QUESTIONS

SF-36v2™ Health Survey© 1996, 2000 by QualityMetric Incorporated and Medical Outcomes Trust. All Rights Reserved.

SF-36® is a registered trademark of Medical Outcomes Trust
(SF-36v2 Standard, US Version 2.0)

Appendix Q. Guidelines to Evaluate Loss of Response and Intolerance to Infliximab

To enroll in this study, subjects who have previously been exposed to infliximab must meet one of the two conditions defined below.

Loss of Response

A subject to have responded to infliximab in the past and subsequently experienced an overall lack of improvement or worsening of symptoms after a full and adequate course of infliximab based on the investigator's assessment.

Intolerance to Infliximab

A subject is defined as intolerant when, in the opinion of the investigator, therapy was discontinued as a result of a significant acute or delayed infusion/administration reaction to the medication.

Table 8.	Potentially Clinically Significant Laboratory Findings (Continued)	40
----------	---	----

List of Figures

Figure 1.	Study Schematic.....	8
-----------	----------------------	---

List of Abbreviations

AAA	Anti-adalimumab Antibody
ADA	Adalimumab
AE	Adverse event
AESI	Adverse event of special interest
ALT	Alanine Transaminase
ANA	Antinuclear Antibody
AST	Aspartate Transaminase
BCG	Bacillus Calmette-Guérin
BUN	Blood Urea Nitrogen
CDC	Centers for Disease Control and Prevention
CRA	Clinical Research Associate
CRF	Case Report Form
CRP	C-Reactive Protein
dsDNA	Double-stranded Deoxyribonucleic Acid
ECG	Electrocardiogram
EU	European Union
eCRF	Electronic Case Report Form
eow	every other week
ew	every week
FDA	Food and Drug Administration
FAS	Full Analysis Set
GCP	Good Clinical Practice
GMA	Granulocyte and Monocyte absorbent Apheresis
GPP	Generalized Pustular Psoriasis
hs-CRP	high-sensitivity C-Reactive Protein
ICH	International Conference on Harmonization
IEC	Independent Ethics Committee
IGRA	Interferon-Gamma Release Assay
IRB	Institutional Review Board
JDA	Japanese Dermatological Association
LOCF	Last Observation Carried Forward
MedDRA	Medical Dictionary for Drug Regulatory Activities

MTX	Methotrexate
NRI	Non-Responder Imputation
PA	Posterior-anterior
PASI	Psoriasis Area and Severity Index
PD	Premature Discontinuation
PGA	Physician's Global Assessment
PK	Pharmacokinetics
POR	Proof of Receipt
PML	Progressive Multifocal Leukoencephalopathy
PPD	Purified Protein Derivative
SAE	Serious Adverse Event
SAP	Statistical Analysis Plan
SC	Subcutaneous
SDP	Study Designated Physician
TB	Tuberculosis
TNF	Tumor Necrosis Factor

3.0 Introduction

This statistical analysis plan (SAP) describes the statistical analysis to be completed by the AbbVie Global Statistics Department for adalimumab study Protocol M14-193 dated 06 April 2017, that incorporates administrative changes 1,2,3, and 4. (original protocol: 08 June 2015). It provides details to further elaborate statistical methods as outlined in the protocol and describes analysis conventions to guide the statistical programming work.

Unless noted otherwise, all analyses will be performed using SAS version 9.3 (SAS Institute Inc.) under the UNIX operating system or in the PC environment.

4.0 Study Objectives, Design and Procedures

4.1 Objectives

The primary objective is to investigate efficacy, safety and pharmacokinetics of adalimumab in Japanese subjects with Generalized Pustular Psoriasis (GPP).

4.2 Design Diagram

This study is a 52-week trial. The study will include a 30-day screening period, 52-week open-label active treatment period, and a subsequent 70-day follow-up period after the last dose.

Subjects will be Japanese patients diagnosed as GPP with total skin score of at least 3 and erythema with pustule (skin score of at least 1) in Japan Dermatology Association (JDA) severity index of GPP in GPP Medical Care Guideline 2014.

Subjects who meet all the inclusion criteria and none of the exclusion criteria will be enrolled and treated subcutaneously with adalimumab 80 mg at the Baseline for initial dose and then 40 mg eow on and after Week 2 until Week 50. Dose-escalation to 80 mg eow is allowed if subjects have inadequate response (i.e., minimal improvement, unchanged or worsened) on or after Week 8. Dose reduction is not allowed throughout the study period for the dose-escalated subjects.

The primary efficacy variable is the proportion of subjects achieving Clinical Response (CR) at Week 16. CR is defined as the reduction of skin score of at least 1 (if the subject's Baseline skin score is 3) or at least 2 (if the subject's Baseline skin score is 4 or higher) relative to Baseline, according to JDA severity index of GPP in GPP Medical Care Guideline 2014.

Study visits will occur at Baseline (Week 0), Weeks 2, 4, 8, 12, 16, 20, 24, 28, 32, 36, 40, 44, 48 and 52, and at the Premature Discontinuation visit if the subject discontinues prior to Week 52. No open label extension (OLE) study is planned after this 52-week study.

Adverse events will be collected throughout the study. Subjects who complete this study or who decide to withdraw the study participation will have a Day 70 follow-up phone call following their last dose of study drug to determine the status of any ongoing adverse events (AEs) or serious adverse events (SAEs), or the occurrence of any new AEs or SAEs.

Figure 1. Study Schematic

[figure not shown]

Table 1.
Study Activities:

Activity	Screening (Day -30 to Day -1)	Baseline ^a (Day 1)			Wk 2	Wk 4	Wk 8	Wk 12	Wk 16	Wk 20	Wk 24	Wk 28	Wk 32	Wk 36	Wk 40	Wk 44	Wk 48	Wk 52 or Premature Discontinuation	Unscheduled Study Visit	70- Day Call
Informed Consent	X																			
Assign Subject ID Number	X																			
Subject Background	X																			
Inclusion/Exclusion Criteria	X	X ^b																		
Medical/Surgical History	X	X ^b																		
Prior and Concomitant Therapy Assessment	X	X ^b	X	X	X	X	X	X	X	X	X	X	X	X	X	X	X	X		
Alcohol Use	X																			
Tobacco Use	X																			
Physical Exam ^c	X	X	X	X	X	X	X	X	X	X	X	X	X	X	X	X	X	X		
Chest X-Ray ^d /12-Lead ECG ^e	X																X ^f	X ^g		
TB Screening ^h	X																			
Vital Signs	X ⁱ	X	X	X	X	X	X	X	X	X	X	X	X	X	X	X	X	X		
Pregnancy Tests	X ^j	X ^k															X ^k			
General Labs ^l : Blood Chemistry and Hematology	X	X ^m	X	X	X	X	X	X	X	X	X	X	X	X	X	X	X	X ^s		

Table 1. Study Activities: (Continued)

Activity	Screening (Day -30 to Day -1)	Baseline ^a (Day 1)	Wk 2	Wk 4	Wk 8	Wk 12	Wk 16	Wk 20	Wk 24	Wk 28	Wk 32	Wk 36	Wk 40	Wk 44	Wk 48	Wk Discontinuation	Wk 52 or Premature Discontinuation	Unscheduled Study Visit	70-Day Call
Urinalysis ⁿ	X	X			X		X				X						X		
HIV Screen ^o	X																		
Hepatitis B Screen ^p	X																		
Hepatitis C Screen	X																		
Antinuclear Antibody (ANA)/Anti-Double-Stranded DNA (dsDNA) ^q	X																		
Photography ^r		X	X	X	X	X	X	X	X	X	X	X	X	X	X	X	X	X	
GPP Skin Score and BSA, Systemic/Laboratory Score	X	X	X	X	X	X	X	X	X	X	X	X	X	X	X		X ^s		
PGA	X	X	X	X	X	X	X	X	X	X	X	X	X	X	X		X ^s		
PASI Score	X	X	X	X	X	X	X	X	X	X	X	X	X	X	X		X ^s		
DLQI		X		X		X		X		X		X		X			X		
SF-36		X		X		X		X		X		X		X			X		
Dispense Study Drug		X	X	X	X	X	X	X	X	X	X	X	X	X	X		X ^s		
Administer Study Drug ^t	X	X	X	X	X	X	X	X	X	X	X	X	X	X	X		X ^s		
PK Measurements ^u	X	X	X	X	X	X	X	X	X	X	X	X	X	X	X		X ^s		
AAA Measurements ^u	X		X		X		X		X		X		X		X		X ^s		

Table 1. Study Activities: (Continued)

Activity	Screening (Day -30 to Day -1)	Baseline ^a (Day 1)	Wk 2	Wk 4	Wk 8	Wk 12	Wk 16	Wk 20	Wk 24	Wk 28	Wk 32	Wk 36	Wk 40	Wk 44	Wk 48	Wk 52 or Premature Discontinuation	Unscheduled Study Visit	70- Day Call
Monitor Adverse Events ^v	X	X	X	X	X	X	X	X	X	X	X	X	X	X	X	X	X	X
Follow-Up Phone Call																		X ^w

Footnote for Table 1:

- The Baseline visit date will serve as the reference for all subsequent visits. A \pm 7-days window is permitted around scheduled study visits.
- Update inclusion/exclusion, medical/surgical history, and prior and concomitant therapy information to assure subject eligibility.
- Physical examinations performed at Screening, Week 24 and Week 52/PD Visits will be full physical examinations. Physical exams performed at all other visits will be symptom-based.
- Chest x-ray (CXR) includes posterior-anterior [PA] **and** lateral views. Subjects with normal chest x-ray within 90 days of Screening will not require a repeat chest x-ray, if documentation is available.
- Subjects with normal ECG within 90 days of Screening will not require a repeat ECG, if documentation is available.
- Subjects will have a repeat CXR or ECG at Week 52 or the appropriate Premature Discontinuation visit, only if in the opinion of the investigator, clinically significant AEs develop during the study that warrant a repeat.
- Subjects can have a repeat CXR/ECG at any time during the study as warranted based on the opinion of the Investigator.
- Subjects with negative latent TB test(s) (In case a subject received both a PPD test and IGRA, both must be negative) within 90 days of Screening will not require a repeat latent TB test, if documentation is available. PPD skin test is to be read 48 to 72 hours after placement.
 - Height will be measured at the Screening only.
 - All females of childbearing potential will have a serum pregnancy test at the Screening that is performed at the central laboratory.

Table 1. Study Activities: (Continued)

- k. All females of childbearing potential will have a urine pregnancy test at the Baseline and Week 52 or Premature Discontinuation visits at the central laboratory. Any subject with a positive urine pregnancy test must have a negative serum test performed at the central laboratory prior to start of the treatment in the study. Urine pregnancy test at the Baseline will be performed also at site to confirm negative result on site. If the result at site is positive, treatment with study drug should not be started until the serum pregnancy test at the central laboratory is confirmed negative.
- l. Subject should be fasting. Please refer to the laboratory manual for further instructions.
- m. Laboratory assessments will only need to be repeated at the Baseline if the time between blood sampling for Screening and Baseline is greater than 14 days, or if the subject's health status has changed to warrant a repeat test.
- n. Dipstick urinalysis will be conducted by the central laboratory at all required study visits. A microscopic analysis will be performed in the event the dipstick results show protein, ketones or blood greater than negative or glucose greater than normal.
- o. Subjects will be tested for HIV and documented that the test has been performed. This testing is to be done at the central laboratory. A subject will not be eligible for study participation if test results indicate a positive HIV infection. AbbVie will not receive results from the testing and not be made aware of any positive result.
- p. Subjects will be tested for the presence of the Hepatitis B Virus (HBV) at Screening. A positive result for the hepatitis B surface antigen (HBs Ag) will be exclusionary. Samples that are negative for HBs Ag will be tested for surface antibodies (HBs Ab) and core antibodies (HBc Ab Total). Subjects with HBs Ag (-), HBs Ab (-), and HBc Ab Total (+) require PCR qualitative testing for HBV DNA. Any HBV DNA PCR result that meets or exceeds detection sensitivity will be exclusionary.
- q. Anti-dsDNA will be measured if ANA is positive.
- r. Photographs of skin lesion will be taken at the time points above in subjects who agree to do in the pre-selected sites.
- s. When dose escalation is decided on unscheduled visit or on any visit when the data collection is not planned, the investigator must assess skin lesion (GPP skin score, BSA, PGA and PASI score), and perform blood sampling for laboratory test and PK/AAA prior to dose escalation. Body temperature will come from Vital Signs. Additional study drug dispense may be necessary, if appropriate.
- t. Administration of study drug will be performed after all assessments and examinations scheduled for that day have been completed. Study drug will be administered every other week in the investigator's office or at subject's home after training of self-injection to ensure proper technique.
- u. Blood samples for the measurement of adalimumab and AAA concentrations will be collected prior to dosing.
- v. All AEs reported from the time of study drug administration until 70 days following discontinuation of study drug administration will be collected. SAEs and protocol-related nonserious AE will be collected from the time the subject signed the study-specific informed consent until 70 days following discontinuation of study drug administration.
- w. Site personnel will contact all subjects by phone 70 days after the last dose of study drug to determine the status of any ongoing AEs/SAEs or the occurrence of any new AE/SAEs.

4.3 Sample Size

GPP is designated as the specified rare and intractable disease in Japan and patient number is quite limited. Assuming the Clinical Response rate of adalimumab in GPP is similar to PASI 75 response in plaque psoriasis, 50% to 60% as expected response rate in adalimumab treatment and 10% as a threshold response rate is hypothesized.

A sample size of 6 to 10 provides over 90% power to detect the difference between expected Clinical Response rate (50 to 60%) and threshold response rate (with no medication, 10%) in GPP, using a one sample Chi-square test with 2.5% one-sided significance level. In case of using Fisher's exact test, an exact binomial test with a nominal 0.025 one-sided significance level will have 82% power to detect the difference between the threshold proportion of 10% and the expected proportion of 50%.

Therefore, the target number of subjects is set 10 subjects, taking the study feasibility into consideration.

4.4 Interim Analysis

An interim analysis of the primary endpoint and secondary efficacy variables as well as safety data collected from Baseline through Week 24 will be performed after the last subject in FAS population completes the 24-week period of the study. A database lock will be performed and any discrepant data will be clarified before the lock.

5.0 Analysis Populations

5.1 Definition for Analysis Populations

Full Analysis Set:

Full Analysis Set (FAS) population includes all subjects who complied with GCP and received at least one dose of study drug and had at least one post-treatment efficacy assessment. FAS is the primary population for the efficacy analysis. In general, efficacy analysis will be performed for all subjects regardless dose escalation.

Safety Dataset:

The Safety set consists of all subjects who received at least one injection of study drug.

Dose Escalation Dataset:

This set consists of all subjects who escalated the study dose from 40 mg eow to 80 mg eow on or after Week 8. In order to evaluate the effect of dose escalation, these subjects will be analyzed for the efficacy and safety (AEs only) using the data prior- and post-dose escalation date, separately.

Pharmacokinetic assessments will be conducted on all subjects who were administered at least one dose of study drug and have at least one post-dose sample collected for the determination of serum adalimumab concentration.

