5.5 Treatments

5.5.1 Treatments Administered

Subjects will receive adalimumab 80 mg (2 syringes) at Baseline (Week 0) by subcutaneous injection. At and after Week 2, subjects will receive 40 mg (1 syringe)

every other week (eow) subcutaneously until Week 50. No study drug administration will occur at Week 52.

Dose Escalation

For subjects who meet dose escalation criteria on or after Week 8, 80 mg (2 syringes) doses will be administered subcutaneously every other week until study end. No dose reduction will be allowed after dose escalation throughout the study. The dose escalation criteria are defined as the subjects who do not achieve Clinical Response (i.e., minimal improvement, unchanged or worsened) on or after Week 8 ([Appendix I](#)).

Prior to dose escalation, the observation result of skin lesions (GPP skin score, PGA and PASI score) will be recorded. Blood draw for the laboratory test (including WBC, hs-CRP and serum albumin for systemic/laboratory score) and measurement of pharmacokinetics and AAA will be also performed, prior to dose escalation.

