6.4 Definition of Analysis Windows

Since subjects do not always adhere to the study visit schedule, the following rules will be applied to assign actual visits to protocol-specified visits including early termination visits.

For each study visit mentioned in the protocol, a nominal or target day will be selected to represent the corresponding visit along with a window around the target day. Windows will be selected in a non-overlapping fashion so that a date collected on the CRF does not correspond to multiple visit windows. Moreover, windows will not discard any post baseline measurement recorded on the CRF. If a subject had two or more actual visits in one visit window, the visit closest to the target will be used as the study visit for that window. If two visits are equal distance from the target, then the later visit will be used for reporting.

The protocol specified visits and corresponding time windows used in the analyses are presented in Table 2, Table 3, Table 4 and Table 5.

The following visit windows will be used for the analysis of assessment of each efficacy variables which are collected at baseline visit and Week 52 Visit or early termination (ET).

Table 2.**Visit Windows for Analysis of Efficacy Variables, General Laboratory Parameters (Blood Chemistry and Hematology)**

Scheduled Week	Nominal Day	Time Window (Rx Day Range)
Day 1	1	≤ 1
Week 2	15	2 – 22
Week 4	29	23 – 43
Week 8	57	44 – 71
Week 12	85	72 – 99
Week 16	113	100 – 141
Week 24	169	142 – 211
Week 36	253	212 – 309
Week 52	365	310 – 421

Table 3.**Visit Windows for Analysis of DLQI, SF-36, Laboratory Parameters (Urinalysis)**

Scheduled Week	Nominal Day	Time Window (Rx Day Range)
Day 1	1	≤ 1
Week 8	57	2 – 85
Week 16	113	86 – 141
Week 24	169	142 – 211
Week 36	253	212 – 309
Week 52	365	310 – 421

Table 4. Visit Windows for Analysis of Vital Signs

Scheduled Week	Nominal Day	Time Window (Rx Day Range)
Day 1	1	≤ 1
Week 2	15	2 – 22
Week 4	29	23 – 43
Week 8	57	44 – 71
Week 12	85	72 – 99
Week 16	113	100 – 127
Week 20	141	128 – 155
Week 24	169	156 – 183
Week 28	197	184 – 211
Week 32	225	212 – 239
Week 36	253	240 – 267
Week 40	281	268 – 295
Week 44	309	296 – 323
Week 48	337	324 – 351
Week 52	365	352 – 379

Visit Windows for Dose Escalation Analysis Set

The study days for the analysis of dose escalation effect will be calculated with reference to the dose escalation date.

Study Day = Date of evaluation – date of dose escalation + 1.

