Table 5. Visit Windows for GPP skin score relative to dose escalation

Scheduled Week	Nominal Day	Time Window (Rx Day Range)
Day 1 (= date of dose escalation)	1	≤ 1
Week 2	15	2 – 22
Week 4	29	23 – 36
Week 6	43	37 – 50
Week 8	57	51 – 64
Week 10	71	65 – 78
Week 12	85	79 – 92
Week 14	99	93 – 106
Week 16	113	107 – 120
Week 18	127	121 – 134
Week 20	141	135 – 148
Week 22	155	149 – 162
Week 24	169	163 – 176
Week 26	183	177 – 190
Week 28	197	191 – 204
Week 30	211	205 – 218
Week 32	225	219 – 232
Week 34	239	233 – 246
Week 36	253	247 – 260
Week 38	267	261 – 274
Week 40	281	275 – 288
Week 42	295	289 – 302
Week 44	309	303 – 316

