10.5 Efficacy Subgroup Analysis

The subgroup analysis listed below is planned for the subgroups shown. Proportion of subjects achieving Clinical Response (remission and improvement) at Weeks 16, 24, and 52.

- Dose escalation: (without dose escalation, with dose escalation)
- Previous infliximab experience (infliximab naïve, prior exposure to infliximab)

For all subject in Dose Escalation Set will be summarized as:

- Proportion of subject achieving Clinical Response by dose escalation.

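### In the Dose Escalation set, Clinical Response at the escalation date is 0% by rule, so a later response rate cannot be read as an effect of 80 mg eow

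*SAP*

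**What the plan says.** SAP 5.1 defines the set: "This set consists of all subjects who escalated the study dose from 40 mg eow to 80 mg eow on or after Week 8". It then gives the purpose: "In order to evaluate the effect of dose escalation, these subjects will be analyzed for the efficacy and safety (AEs only", to be done "using the data prior- and post-dose escalation date, separately".

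SAP 10.5 lists one efficacy output for the set: "Proportion of subject achieving Clinical Response by dose escalation".

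The entry rule is in Protocol 5.5.1: "The dose escalation criteria are defined as the subjects who do not achieve Clinical Response", applied on or after Week 8. Appendix I puts the same rule in category terms: only minimal improvement, unchanged or worsened qualifies.

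SAP 6.4 counts study days from the date of escalation. Table 5 has one row for everything up to that date, "Day 1 (= date of dose escalation", with range Day 1 or earlier, followed by two-weekly rows from Week 2 to Week 44. If several visits fall in one window, "the visit closest to the target will be used as the study visit for that window". Protocol 5.5.1 has the skin lesions recorded before escalation, and footnote t to the Study Activities table places dosing after that day's assessments.

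SAP 10.1 makes the efficacy analysis descriptive, with no significance level and with exact 95% confidence intervals for proportions.

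**The concern.** The set is selected on the variable that it then summarises. A subject becomes a member by not being in Clinical Response, and the pre-escalation reading assigned to that subject is the one on which membership rests. The starting rate therefore reflects the entry rule and carries no separate information about response on 40 mg eow.

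SAP 5.1 nevertheless states the purpose as evaluating an effect, and neither 5.1 nor 10.5 adds a caution. In a single-arm trial, a move from 0% to some positive rate invites the conclusion that 80 mg eow produced it. Recovery in a disease that Protocol 3.0 describes as recurring, or late response to 40 mg eow, would give the same picture.

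**Working it through.** **Plan's own figure.** The documents give no figure for this set: no expected number escalated and no response rate after escalation. The one exact figure in SAP 4.3 (82% power, 10% against 50%) reproduces at N = 10. Requiring at least 4 responders gives a one-sided error of 1.28% and power of 82.8%. It does not bear on this point.

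**Step 1: the pre-escalation rate.** Let m be the number escalated.
- Entry requires no Clinical Response (Protocol 5.5.1, Appendix I).
- The pre-escalation window is Day 1 or earlier with target Day 1 (SAP Table 5), and the closest visit is used (SAP 6.4). The value kept is therefore the assessment at or nearest escalation.
- If the rule is followed, the rate is 0/m = 0%.

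**Step 2: possible changes.** The later rate is x/m with x between 0 and m. The change x/m - 0 is zero or positive and cannot be negative.

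**Step 3: size if 80 mg eow adds nothing.** Let q be the chance that a subject who failed Clinical Response at escalation is a responder at one given later visit on an unchanged dose. Treat subjects as independent. The documents give neither q nor m, so both are assumed and shown as ranges.
- Expected change = q.
- P(0% to 0%) = (1-q)^m.
- P(apparent gain) = 1-(1-q)^m.

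For example, with q = 20% and m = 5: (0.8)^5 = 0.328, so P(apparent gain) = 67%.

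| q | m = 3: gain / null | m = 4: gain / null | m = 5: gain / null |
|---|---|---|---|
| 10% | 27% / 73% | 34% / 66% | 41% / 59% |
| 20% | 49% / 51% | 59% / 41% | 67% / 33% |
| 30% | 66% / 34% | 76% / 24% | 83% / 17% |

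At q = 0 the result is always 0% to 0%. These figures are for one later visit. Reading the best of several visits makes a gain at least as likely, while counting missing values as not achieved (SAP 6.5) works the other way.

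**The case against.** **The pre-escalation value is not defined in words.** SAP 5.1 speaks of data before the escalation date, which could include earlier visits at which a subject was in response. The rate would then not be fixed at 0%, and a fall would be possible. This stands as an ambiguity, but Table 5 and the closest-visit rule point to a single value at escalation. If the wider reading were meant, the sign of the change would depend on a reference that the SAP leaves open. Either way the text needs an edit.

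**The summary is descriptive.** No before/after difference or test is specified, and SAP 10.1 sets no significance level. The effect of escalation is not a stated objective. This stands and limits the weight of the point. It does not remove the stated purpose in SAP 5.1.

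**Late response may be rare.** Protocol 5.6.4 says that mean PASI change in plaque psoriasis was close to steady by Week 8, so q could be small. That is a group mean in another form of the disease and does not settle q for individual GPP subjects. A small q is still possible, and the table shows that a null result is then the likelier one.

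**Other measures are available.** SAP 5.1 refers to efficacy in general, Table 5 is titled for GPP skin score, and PGA and PASI are also recorded before escalation. These have no 0% floor, although selection at a poor reading can bias them too. Clinical Response is therefore not the only within-subject information on the escalated dose.

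**Stronger readings.** A reader might infer that the comparison can never show a null, or always shows a gain. That is wrong: 0% to 0% has probability (1-q)^m. A reader might also infer that subjects are escalated at their first failing visit. The documents say that escalation is allowed, not required, so its timing is not fixed.

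**Conclusion.** The point holds in a limited form. If the escalation rule is followed and the Table 5 value is used, the pre-escalation Clinical Response rate is 0% by construction. The change cannot be negative and is biased upward by q when 80 mg eow adds nothing. For 3 to 5 escalated subjects, an apparent gain with no dose effect has probability 49% to 67% at q = 20% and 66% to 83% at q = 30%. The direction follows from the documents. The size rests on assumed q and m and on independence between subjects.

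The documents do not support reading this as a flaw in the primary result. That analysis uses the FAS regardless of escalation and is untouched. What is affected is any statement that the response rate after escalation shows what 80 mg eow achieved. This is an inexpensive improvement that should be made.

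**What to change.** In SAP 5.1, replace the purpose clause with wording such as *to describe the course after escalation*. Add that Clinical Response at Day 1 of Table 5 is 0% by the escalation rule, is not a comparator, and that a later response rate is not attributed to 80 mg eow.

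In SAP 10.5, present for each escalated subject the total skin score and Clinical Response at all visits before and after escalation, with the escalation date marked. This shows whether a subject had responded earlier, was improving slowly or was fluctuating, all of which a single pre-escalation value hides.

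The cost is a few lines of SAP text and one listing or plot from data already collected. No dosing rule, visit or endpoint changes. The trial gives up a before/after effect claim for the escalated dose, which this design cannot support.
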